11. CANDIDATE IDENTIFICATION AND PROCEEDINGS

Patient recruitment will primarily be done through the use of UCSF electronic health record (EHR) recruitment services from the Clinical and Translational Service Institute (CTSI) to assist with targeting and identification of potentially eligible participants. As an "honest broker" of the EHR data, the service is designed to protect patient privacy and offer more efficient way to recruit eligible participants that meets the study's inclusion/exclusion criteria. The cohort of patients scheduled to receive physical therapy services will be identified and pre-screened by CTSI to ensure potential participants are eligible to meet the initial study's criteria. Once patients have been identified, they are flagged from their appointments for physical therapy services at the UCSF Outpatient Faculty, and will be evaluated in-person as part of their regular initial scheduled visit (i.e. evaluation visit). At the time of this visit, potential participants will be assessed by one of the co-investigators to also ensure that participants meet the cognitive and mental capacity

requirements. Once the criteria are met, investigator will present the study and invite the patient to participate and provide consent. The participant's screening survey data will be collected and be randomized to one of the two arms, coordinated by the study coordinator. All study-related information will be stored by electronic data capturing (EDC) system.

To centralize all study-related information, a commercially available electronic data capturing (EDC) system will be used.

Following the identification of a potential candidate, the investigator will enter the EDC portal and fill the screening survey. If the patient is eligible (i.e. meets inclusion criteria and does not have any exclusion criteria) the investigator will present the study and invite the patient to participate and provide consent.

12.PROCESS OF CONSENT

The study will be presented verbally to potential participants by a study investigator, in a face-toface meeting. Adequate time will be allowed for the candidate to clarify any doubts about the study, following which the eConsent form will be sent through the EDC platform to the participant and investigator, for signature. The study consent form (Annex 1) will then be signed by the participant and the investigator collecting consent, and stored in the EDC platform.

13. Allocation & Blinding

Patients will be randomly allocated to one of two groups, using random permuted blocks of 6. After eConsent collection, the investigator will enter the EDC portal and proceed with randomisation (also built into the EDC). Following randomisation, the investigator will contact the person responsible for the rehabilitation program in each group to allocate the participant to the respective study arm. Blinding of investigators and patients regarding allocation arm will not be possible, given the nature of the intervention. Analysis of study results will be performed by an independent statistician at UCSF.

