7. STUDY DESIGN

Prospective, single-center, parallel-group, randomised controlled study.

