9. SAMPLE SIZE ESTIMATION

Sample size estimation calculations were performed taking into consideration the primary outcome measure – the QuickDASH. In a sample of 57 patients with shoulder tendon disorders treated with SWORD Health's medical device in the context of work-related conditions, the mean and standard deviation of the QuickDASH scale at baseline was of 59 and 19 points respectively. A Minimal Detectable Difference (MDD) of 11.2 points was considered, based on the psychometric properties of the scale.⁵⁶ Considering a power of 80%, a two-sided 0.05 significance level and a 10% dropout rate, 80 (40+40) patients would be necessary to detect a 11.2 points difference between the two groups.

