ANNEX 3- CONVENTIONAL PT INTERVENTION PROTOCOL

The co-investigators are encouraged to use the McClure's staged based rehabilitation therapy (STAR) classification (see Table 1) as a *guide* but not necessarily as a prescriptive manner to select interventions. Instead, the co-investigators will reference their use interventions categorized based on commonly practiced in an outpatient physical therapy setting (see Table 2).

McClure's stage-based rehabilitation therapy (STAR) intervention approach is based on the Irritability of the patient's condition. Assessments of symptoms of Irritability are gathered from the patient's history and findings from the examination. Table 1 represents a guided approach to STAR for the chronic shoulder pain population and the type of interventions used. Table 2 describes the type of commonly used physical therapy interventions that could be used in the cohorts.

Guideline to help determine the stage of Irritability is based on both history and examination findings*

High	Moderate	Low
• Pain >= 7/10	• Pain (4-6/10)	• Pain (<= 3/10)
• Consistent night or	• Intermittent night or rest pain	• Absent night or rest pain
resting pain	• Pain at end of range	• Minimal pain with overhead
• Pain before end of range	• AROM and PROM close	• AROM = PROM
• AROM < PROM	• Moderate disability	• Low disability
• High disability		
Approach: Minimize	Approach: Mild-moderate physical	Approach: Mod-high physical
physical stress	stress	stress
• Activity	Basic-level functional	• High-demand functional
modification	activity restoration	activities

*Taken from Staged approach (STAR) for rehabilitation classification by McClure et al.

Table 1. McClure's staged approach to shoulder intervention based on different impairments

Impairments	Irritability	Intervention	Examples of
		Approaches	Intervention**
Restricted passive mobility	Low	• ROM	• Aggressive active and
due to joint/muscle/neural		• Stretching	passive stretches (e.g.,
tissues		• manual therapy:	sleeper stretches;
		tolerable stretch	foam roller T's, Y's,
		sensation at end-	I's; Doorway stretch)
		range	
		Hold longer	
		duration and	
		frequency	
Restricted passive mobility	Moderate	• ROM	• Active and passive
due to joint/muscle/neural		• Stretching	stretches (e.g., gentle
tissues		• Comfortable end-	sleeper stretches;
		range manual	Foam roller T's, Y's,
		therapy	I's; modified to $\frac{1}{2}$ to
			full foam roller T's,
			Y's, I's; Modified
			doorway stretch)

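### One fixed, disclosed block size of 6 in an open single-centre trial could let an enroller who tracks all earlier allocations know about a quarter of assignments in advance; randomly varying block sizes would remove most of that certainty

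*Combined protocol and SAP*

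**What the plan says.** Section 13 (Allocation & Blinding) names one block size: patients are allocated "using random permuted blocks of 6". No other size is mentioned, and nothing says the size is withheld from enrolling staff. Section 7 describes the trial as "Prospective, single-center, parallel-group, randomised controlled study", and no stratification factor is given anywhere, so there is a single list.

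On who does what:

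- Section 11 has one of several co-investigators assess the patient at the scheduled evaluation visit, present the study and invite participation.
- Section 12 has a study investigator collect consent.
- Section 13 continues that, once consent is signed, "the investigator will enter the EDC portal and proceed with randomisation".
- That person then learns the arm: "Following randomisation, the investigator will contact the person responsible for the rehabilitation program in each group" to place the patient.
- Section 11 adds that the study coordinator coordinates randomisation.
- On masking, section 13 states: "Blinding of investigators and patients regarding allocation arm will not be possible, given the nature of the intervention".
- Annex 3, on the control treatment, begins "The co-investigators are encouraged to use" a staged classification as a guide for choosing interventions. Co-investigators therefore appear to be involved in control-arm care as well.

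Section 9 gives the planned size: "80 (40+40) patients would be necessary to detect a 11.2 points difference between the two groups".

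**The concern.** With a constant block size, the last places in a block are determined once one arm has used its three places. Holding the list inside the EDC hides the list. It does not stop someone who knows the block size and the past arms from working out the next one, and in an open trial the past arms are visible.

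An enroller who knows the next arm has some room to act on it. The pain-duration criterion in section 10 and the in-person capacity assessment in section 11 both involve judgement, as does how the study is presented. The primary outcome (section 8.1) is a self-reported questionnaire, and the main comparisons in section 16 are t tests or Mann-Whitney tests without covariate adjustment. The study hypothesis is that the digital arm does at least as well, so a shift well below 11.2 points could still affect the conclusion. Selective enrolment is hard to detect or repair once it has happened.

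**Working it through.** **Inputs.** Block size 6 (section 13). Ratio 1:1, hence 3+3 per block, inferred from the 40+40 split in section 9. List length 80 (section 9). One centre, one list (section 7). The shift e is not in the documents; I assume 2 to 5 QuickDASH points.

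**The plan's own figure.** The documents give no figure for predictability, so there is none to reproduce. The 80 is used here only as the list length. The section 9 inputs (11.2 points, SD 19, 80% power, two-sided 0.05) give 46 per arm, or 52 per arm (104 in total) after 10% dropout, not 80. That is a separate matter and makes no difference here: with 104 patients the certain share would be 17 × 1.5 / 104 = 24.5%.

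**Certain allocations, fixed blocks of 6.** There are C(6,3) = 20 equally likely sequences. The next arm is certain when one arm already has 3:

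- position 4: 2/20 = 10%
- position 5: 8/20 = 40%
- position 6: 100%

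The sum is 1.5 per block, or 1.5/6 = 25%. In 80 patients there are 13 full blocks plus 2 patients whose arms are never certain: 13 × 1.5 = 19.5, and 19.5/80 = 24.4%.

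**If allocations are not shared.** Simulated lists of 80, with patients split at random among k enrollers who see only their own allocations but know the block boundaries, gave:

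| Enrollers | Certain allocations |
|---|---|
| 1 (or full sharing) | 24.4% |
| 2 | 3.0% |
| 3 | 0.9% |

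**Best guess, fixed blocks of 6.** Guess the arm with fewer patients so far. The chances of being right at positions 1 to 6 are 0.5, 0.6, 0.6, 0.7, 0.7 and 1.0. They sum to 4.1, and 4.1/6 = 68.3%. Over 80 patients: (13 × 4.1 + 0.5 + 0.6)/80 = 68.0%.

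**Randomly varying sizes 4, 6 and 8.** Simulated lists of 80, with an observer who knows the set of sizes but not their order, gave about 2.4% certain allocations and 67.9% best-guess accuracy. An observer who knows no sizes and only counts arms was right 67.9% of the time, against 68.0% under fixed 6. Every completed block returns to balance, so a running count is enough to guess with.

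**Upper bound on bias.** Suppose a share f of each arm is enrolled with certain knowledge, and those patients average e points better in one arm and e worse in the other. The arms then differ by 2 × e × f.

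| Scenario | Formula | e = 2 | e = 5 |
|---|---|---|---|
| Fixed 6, all allocations known | 2e × 0.25 | 1.0 | 2.5 |
| Fixed 6, two enrollers, no sharing | 2e × 0.03 | 0.1 | 0.3 |
| Sizes 4, 6, 8, all allocations known | 2e × 0.024 | 0.1 | 0.2 |

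If every best guess were acted on, the bound would be 2e(2 × 0.683 − 1) = 1.5 to 3.7 points. That component is essentially the same under either scheme.

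For scale, with SD 19 and 36 completers per arm (40 less 10%), the standard error of the difference is 19 × √(2/36) = 4.5 points. The 1.0 to 2.5 points are about 0.2 to 0.6 of that.

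**The case against.** Fixed blocks of 6 are a common choice and contradict nothing else in the plan. The case against goes further on five counts.

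- **Several enrollers.** Section 11 speaks of one of the co-investigators, so there is more than one. Without sharing, certainty nearly disappears. This stands as a condition on the size. Sharing is plausible (one clinic, open treatment, one coordinator) but is not documented.
- **Limited discretion.** Patients are pre-screened from the health record and flagged from appointments already scheduled, and randomisation follows consent in the EDC. This narrows the freedom to time an offer. It does not prevent inference of the next arm, or judgement on eligibility and presentation.
- **Baseline.** A reader might infer that any selection feeds undiminished into the treatment difference. The documents do not support that. Section 8.1 defines the outcome between baseline and 8 weeks, and section 16 analyses change from baseline and adds a repeated measures ANOVA. These would partly offset selection on baseline severity. They would not offset selection on expected response or motivation.
- **Unsourced shift.** The 2 to 5 points have no source in the documents, and the bound assumes that every certain allocation is exploited. It is a ceiling, not an expected bias.
- **Guessing survives the remedy.** A reader might infer that concealing the sizes defeats guessing. It does not, because counting arms works without knowing any size. This stands and limits what the change can claim.

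**Conclusion.** The point holds as a weakness in allocation concealment, with moderate confidence. For someone who knows all earlier allocations, a fixed 3+3 block makes 24 to 25% of assignments certain (about 19.5 of 80). The share is about 3% or 1% if two or three enrollers share nothing. The bias ceiling is 1.0 to 2.5 QuickDASH points under the assumed shift, before any offset from the change-from-baseline analysis.

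A reader might go further and conclude that investigators will know a quarter of allocations, or that the comparison will be biased. The documents support neither: they do not give the number of enrollers or say what each sees, and nothing in them suggests that anyone would act on a prediction. The result also rests on the 1:1 ratio within blocks, which is inferred, and on reading the consenting and randomising investigator in sections 12 and 13 as the same person, which is the natural reading. The change is worth making because it is nearly free and the problem cannot readily be corrected afterwards.

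**What to change.** In section 13, replace "using random permuted blocks of 6" with *permuted blocks of randomly varying size*. Program this in the EDC, for example sizes 4, 6 and 8 in random order. Keep the sizes in a restricted randomisation specification that recruiting and treating staff do not see. Certain allocations then fall from about 24% to about 2%, even if the set of sizes becomes known. Describe the change as removing near-certain prediction only; best-guess accuracy remains near 68%.

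The cost is one sentence and one EDC setting, with no extra patients or staff. The arms may end slightly unequal. A block of 8 cut off after four patients in the same arm gives at worst 42 against 38, equivalent to 2/(1/42 + 1/38) = 39.9 per arm, so the effect on power is negligible. The present scheme does not guarantee 40+40 either: 80 is not a multiple of 6, and the last two patients can fall in the same arm, giving 41 against 39.

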14. INTERVENTION

a. Digital program

Patients in the digital intervention group will benefit from an 8-week program composed of therapeutic exercise, education and cognitive behavioural therapy (CBT) program provided by SWORD Health. These patients will be referred to SWORD Health by the investigator who identified the candidate. SWORD Health will then assign a physical therapist to each patient. The physical therapist will contact the patient for onboarding and will manage the case.

Patients in this group will performed home-based rehabilitation sessions using SWORD Phoenix[®], under remote monitoring by a physical therapist. Participants will be provided with a tablet computer with a SWORD mobile app installed, along with two inertial motion trackers (each comprised of a gyroscope, an accelerometer and a magnetometer) to be placed on chest, upper arm and wrist, respectively. These trackers enable precise movement quantification, feeding the mobile app, which guides the patient through the session, providing video and audio instructions before each exercise, as well as real-time audio and video biofeedback during the exercise. On the other end, the clinical teams are allowed to remotely monitor results and prescribe/edit exercise sessions through a web-based portal.

The exercise component will follow the protocol outlined in **Annex 2**, which can however be adapted by the physical therapist to the specific needs of the participant. Participants will be asked to start with three 20 min sessions per week, building gradually to three 30 min sessions per week. Participants will not be excluded from the study in case of lower adherence, but will not be included in the per-protocol analysis if they perform less than 21 sessions over the course of 8 weeks.

Participants in this group will be considered as dropouts if they: a) choose to abandon the study;b) do not engage in any exercise session for at least fourteen consecutive days.

The educational component will be delivered automatically through a smartphone app (available for iOS and Android), and will take the form of small educational texts that will be released

periodically to the participant. This component is not mandatory per protocol, but metrics on user engagement will be measured.

The CBT program will take the form of a self-paced program consisting of written and prerecorded audio materials. An email will be sent weekly by the physical therapist to the participant, during the 8 weeks of the program. Each email will contain an introductory text describing the objectives for that week, as well as a link to that week's audio session and a PDF attachment with self-guided exercises. The CBT component is not mandatory per protocol, but metrics on user engagement will be measured.

b. Conventional PT

Patients in this group will benefit from a 8-week program consisting of two 30 min face-to-face PT sessions per week in an outpatient clinic setting, for a total of 16 sessions. The program will follow the principles outlined in **Annex 3**, which includes commonly used interventions adapted by the physical therapist to the specific needs of the participant.

Participants in this group will be excluded from the per protocol analysis if they complete less than 14 sessions over 8 weeks. Participants in this group will be considered as dropouts if they: a) choose to abandon the study; b) miss four consecutive scheduled PT sessions.

In addition to the face-to-face sessions, PTs will also be communicating with participants in this group through a secure messaging system (Mychart) used at UCSF or, alternatively, through a telephone check-ins (10-15 min calls, up to twice per week).

15. PARTICIPANT ASSESSMENTS

Patients will be assessed at baseline, 4 and 8 weeks.

Baseline Assessment

This assessment will involve a face-to-face visit, where the following information will be collected:

- a) date of birth
- b) gender
- c) height & weight
- d) body mass index
- e) formal education (years of schooling)
- f) job type
- g) previous shoulder surgery (> 3 months ago)
- h) Working status
- i) Geocodes/zip
- j) Race/ethnicity
- k) Age

The following outcomes will also be assessed in this visit: a) Shoulder Range of Motion; b) PROMIS CAT measures.

Shoulder Range of Motion will be measured in the following movements: 1) shoulder flexion; 2) shoulder abduction; 3) external rotations with shoulder abducted at 90 degrees. The participant will be asked to perform three non-painful repetitions of each movement, in a standing position. The investigator will measure the maximum joint angle attained by the participant, using a digital goniometer in each repetitions. The highest of the three values will be considered.

Regarding satisfaction with social role and ability to participate in social roles and activities, these will be collected through PROMIS CAT v2.0. These will be collected onsite, and the results will then be transferred by the investigator to the eCRF.

Assessment of primary outcome, as well as the remaining secondary outcomes will be performed through an electronic questionnaire to be filled by participants, through the EDC system. These will need to be filled within 5 consecutive days, counting from the date they are sent to the participant. To promote compliance with this schedule, whenever the deadline is approaching, automatic email reminders will be sent to participants. Participants will be excluded from the study

for protocol breach in case they don't fill in the assessment forms. Upon completion of the baseline form, participants in the study will receive a stipend of \$25.

Additional measurements of upper limb function and tri-dimensional motion will also be performed at the onsite visit by the clinician, using a motion capture system. These will not be considered in the outcomes of this study, but will be made available for post-hoc analysis.

Interim assessment (4 weeks)

Participants will be required to complete a questionnaire similar to the baseline assessment, within a 5-day window beginning at the start of week 4. These assessments will include all the information pertaining to the primary and secondary outcomes, except for those that are collected through a face-to-face assessment. These (shoulder range of motion and PROMIS CAT measures) will not be collected on this assessment. Upon completion of this form, participants in the study will receive a stipend of \$25.

Final assessment (8 weeks)

This assessment will involve a face-to-face visit, where the following outcomes will be assessed: a) shoulder Range of Motion; b) PROMIS CAT measures and c) Participant satisfaction (Net Promoter Score). Shoulder Range of Motion and PROMIS CAT measures will be assessed using a similar methodology to the one descried for the baseline assessment.

Participants will also be required to complete a questionnaire similar to the baseline and interim assessments, within a 5-day window beginning at the start of week 4. These assessments will include all the information pertaining to the primary and secondary outcomes, except for those that are collected in the face-to-face visit. Upon completion of this form, participants in the study will receive a stipend of \$25.

Additional measurements of upper limb function and tri-dimensional motion will also be performed at the onsite visit by the clinician, using a motion capture system. These will not be considered in the outcomes of this study, but will be made available for post-hoc analysis.

Engagement assessment

For participants on the digital group, engagement and usage metrics of the educational and CBT components will also be collected automatically.

Additionally, the following activity log will be collected from patient's Electronic medical records and time stamps, as well as paper survey (or, in the case of the digital group, sent to the study coordinator via email, with the participant identified only by the study ID), to be entered into EDC portal by study coordinator:

- 1. Face-to-face visits registry (dates, times and duration)
- 2. Remote sessions registry (dates, times and duration)
- 3. Number and duration of contacts between PT and participant (emails, text messages, phone and videocalls)
- 4. Total time spent on remote monitoring of the patient (digital group only)

Adverse events

In any event during the course of the study if subjects experience adverse effects of both internal (on-site) and external (off-site) events, a prompt reporting to the UCSF Human Research Protection Program (HRPP)/institutional review board (IRB) and to the sponsor of the study will take place. This includes any unanticipated problems involving risk to subjects noted in the study. The safety plan in IRB will contain protocol to help with communication and procedures that are in place to monitor and report adverse events should they occur. The investigators will accurately document causality assessment to their best knowledge and follow-up of all definite, probable, or unrelated adverse events to the study and safety-related information.

Care continuity

To ensure that quality of care is not compromised throughout the study, all subjects from both

groups will be assessed at the final appointment to determine whether further care is warranted. If subjects require additional physical therapy services or follow-up back to the physician, the primary investigator will coordinate with UCSF physical therapist to ensure continuity of care or proper closure of their care are complete.

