8. STUDY OUTCOMES

8.1 Primary Outcome

Impact on physical function and symptoms measured through the shortened Disabilities of the Arm, Shoulder and Hand questionnaire (QuickDASH) between baseline and 8 weeks.

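### The plan does not place the baseline QuickDASH before randomisation or confine the missed-form exclusion to that period, and it dates the 8-week form from week 4

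*Combined protocol and SAP*

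**What the plan says.** **Order of events.** Section 11 names one data item ahead of allocation: the participant's "screening survey data will be collected and be randomized to one of the two arms". Section 13 gives the trigger: "After eConsent collection, the investigator will enter the EDC portal and proceed with randomisation (also built into the EDC". The next step is also in Section 13: "Following randomisation, the investigator will contact the person responsible for the rehabilitation program in each group to allocate the participant". The same section adds: "Blinding of investigators and patients regarding allocation arm will not be possible".

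**How the primary outcome is collected.** Under Baseline Assessment, Section 15 lists demographics, range of motion and PROMIS CAT for the face-to-face visit. QuickDASH is not on that list. Instead: "Assessment of primary outcome, as well as the remaining secondary outcomes will be performed through an electronic questionnaire to be filled by participants". Participants have five consecutive days from the sending date to return it, with email reminders. The sending date is not tied to consent, to the visit or to randomisation.

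**Missed forms.** The same subsection removes participants from the study "for protocol breach in case they don't fill in the assessment forms". The sentence that follows it concerns the stipend for the baseline form.

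**Final form.** Under the 8-week heading, Section 15 opens the questionnaire's five-day window at the beginning of week 4, as it does for the interim form.

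**Use in the analysis.** Section 8.1 defines the primary outcome on the "questionnaire (QuickDASH) between baseline and 8 weeks". Section 16 looks at both the 8-week value and change from baseline, adds a repeated measures ANOVA, and promises intention-to-treat (ITT) and per-protocol analyses. It does not define the ITT set.

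**The concern.** QuickDASH is self-reported and the patient cannot be blinded. If the baseline form is returned after the patient has heard the allocation, the answer may be coloured by satisfaction or disappointment with the arm. A between-arm shift of that kind is not a treatment effect, but it passes point for point into change from baseline. It also enters the group-by-time term of the repeated measures ANOVA if baseline is one of the time levels.

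The exclusion sentence raises a second problem from the same gap. If randomisation needs only consent, someone who never returns the baseline form may already hold an allocation. Removing that person is a post-randomisation exclusion, and if return rates depend on the arm, the groups compared are no longer those that were randomised.

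The third item is a contradiction in timing. The only window written for the primary end-point form falls at week 4, while the end point is at 8 weeks.

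**Working it through.** **1. Is the order fixed anywhere?** Side by side:

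| Section | Stated | Not stated |
|---|---|---|
| 11 | Screening survey, then randomisation | Baseline questionnaire |
| 13 | Randomisation after eConsent; arm lead then contacted | Any wait for a completed form |
| 15 | QuickDASH by electronic form, five days from sending | When it is sent relative to randomisation |

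No section requires the form first, and none says it comes afterwards. The order is open.

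**2. What a baseline shift would do.** From Section 9: SD 19 (a baseline value), 40 per arm, 10% dropout, two-sided 0.05. Analysed per arm: 40 × 0.9 = 36. Assumed, because the documents do not give them: SD 19 also at 8 weeks, correlation r between the two times, a between-arm baseline shift s, and no true difference.

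The plan's own total of 80 does not reproduce at its stated two-sided 0.05. For 11.2 points at SD 19 the normal formula gives 46 per arm, or 52 after dropout, 104 in all. One-sided 0.05 gives 36, then 40 per arm, which is 80. That is a separate matter; 36 per arm is used here only as the number the plan expects to analyse.

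- SD of change = 19 × √(2(1 − r)). At r = 0.5 this is 19.0.
- Standard error of the difference = 19.0 × √(2/36) = 4.48.
- Noncentrality = s / 4.48, referred to a two-sided t test on 70 degrees of freedom.

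| Shift s (points) | r | SD of change | False-positive rate, change score |
|---|---|---|---|
| 0 | any | – | 0.050 |
| 1 | 0.5 | 19.0 | 0.056 |
| 2 | 0.5 | 19.0 | 0.073 |
| 5 | 0.5 | 19.0 | 0.196 |
| 5 | 0.3 | 22.5 | 0.154 |
| 5 | 0.7 | 14.7 | 0.296 |

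The raw 8-week comparison does not use baseline, so s moves it by 0 points.

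**3. What the exclusion rule could add, read as covering the baseline form only.** Let q be the share of would-be 8-week returners removed in an arm, and g their 8-week gap from those retained. The between-arm bias has size |g₁q₁ − g₂q₂|. With equal q and g in both arms it is 0. Assuming q of 15% against 5% and g of 5.6 to 11.2 points in both arms: 0.10 × 5.6 = 0.56 and 0.10 × 11.2 = 1.12 points, in either direction. This applies only to the raw 8-week comparison, because a person with no baseline has no change score whether or not the rule exists.

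**4. The week-4 window.** Section 8.1 sets the end point at 8 weeks; the final-assessment text in Section 15 sets the form at the start of week 4. Conventional care is "two 30 min face-to-face PT sessions per week in an outpatient clinic setting, for a total of 16 sessions". Taken literally, the form would fall after 3 × 2 = 6 of 16 scheduled sessions, or 4 × 2 = 8 if week 4 means four weeks after the start. The two statements cannot both be followed.

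**The case against.** The best defence is that the word baseline ordinarily means before randomisation, and that requiring consent first does not rule out a completed form between consent and allocation. An electronic form with a five-day limit could also be filled in during the visit. This stands as far as it goes. A reader might infer that the protocol prescribes a baseline taken after allocation, and the text does not support that. What remains is that the only written sequence leaves the form out.

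A reader might also take the exclusion sentence to cover the 4- and 8-week forms, since it speaks of forms in the plural and sets no time limit. That reading is weak. The sentence sits under Baseline Assessment, the later questionnaires carry no such penalty, and several instruments at baseline would account for the plural. The narrower reading is enough for the point, because a baseline non-returner may already be randomised.

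Nor should a loss of power be charged to the rule. Without a baseline, a participant is already absent from change-score and complete-case ANOVA results, so any loss due to the rule is confined to the raw 8-week comparison. Section 9 does not define its 10% dropout, which may already include non-return.

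The conflict with ITT is likewise conditional: it arises only if excluded people are not followed or not analysed. Section 14 keeps low adherers in the digital arm in the study, which suggests that the authors meant to retain participants.

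Finally, the week-4 wording is almost certainly copied from the interim paragraph, and a site would be unlikely to act on it. It needs correcting, but it is not evidence that the end point was meant to move.

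**Conclusion.** The concern holds as an omission and two wording faults on the primary outcome form. The plan leaves open a self-reported baseline given after allocation, does not confine its missed-form exclusion to the time before randomisation, and contradicts its own 8-week time point. The textual gaps are certain; their effect is not.

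The documents give no shift, correlation, miss rate or outcome gap, and zero bias is possible. Under the assumptions shown, a 1- to 2-point shift is a mild disturbance of the change-score test. The larger rates need a shift of 5 points, about 45% of the plan's 11.2-point difference (5/11.2), before any treatment effect. The raw 8-week comparison, which Section 16 also plans, is protected from a baseline shift but not from post-randomisation exclusions.

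This should be put right because the remedy is cheap and the form carries the primary outcome. It does not show that the trial's result would be wrong.

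**What to change.** 1. State in Sections 13 and 15 that the baseline questionnaire must be complete before the EDC will randomise, and treat non-returners as screen failures. Cost: one EDC setting and a sentence of protocol text. The downside is up to five days' delay for some patients and a few more people consented; if 10% did not return the form (an assumption), 80 / 0.9 = 88.9, so about 89 consented to randomise 80. Completing the form on site avoids both but adds visit time, and the plan would have to say that the visit precedes randomisation, which Section 15 does not.
2. Limit the exclusion sentence to the period before randomisation. After it, keep sending the 4- and 8-week forms to all randomised participants who have not withdrawn consent to follow-up, and analyse them in the arm assigned. Define the ITT set that way in Section 16. Cost: a short edit and some additional reminders.
3. Reconcile the 8-week questionnaire window in Section 15 with the 8-week time point in Section 8.1. Cost: an editorial correction.

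Whether to replace the repeated measures ANOVA with a mixed model is a separate, optional question that this point does not depend on.
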